2.4.4 Analyses of efficacy endpoints

2.4.4.1 Analysis of primary efficacy endpoint(s)

2.4.4.1.1 Main statistical model and adjustment of covariates

The primary estimand is the intent-to-treat estimand, the treatment difference between dupilumab and control in the mean percentage reduction of OCS dose at Week 24 while maintaining asthma control of all patients in the ITT population no matter whether the patients discontinue treatment before Week 24 or not. To estimate the estimand, data of patients who permanently discontinue treatment will be incorporated in the primary analysis, and missing data due to patients dropping out from study will be handled by approaches specified in the missing data handling section below

The primary efficacy endpoint will be analyzed using an analysis of covariance (ANCOVA) model. The model will include the percentage reduction of OCS dose at Week 24 as the response variable, and the treatment groups, optimized OCS dose at baseline, regions (pooled countries), and baseline eosinophil level subgroups (<0.15 Giga/L, ≥ 0.15 Giga/L) as covariates. The treatment difference will be tested at the 2-sided significance level of α =0.05. Descriptive statistics for the primary efficacy endpoint will be provided, including the number of patients, means, standard errors, and least squares (LS) means by the treatment groups, as well as the difference in LS means and the corresponding 95% confidence interval (CI). Provided below is sample SAS code for running the model:

```
proc glm data= ocsdata;
     class eosbgp2n cntygr1 trt01pn;
     model ocspcw24 = ocsbl eosbgp2n cntygr1 trt01pn;
     lsmeans trt01pn / stderr pdiff cl;
     estimate 'Diff Dupilumab vs Placebo' trt01pn -1 1;
     ods output LSMeans=lsmeans Estimates=lsmeandiff
                 LSMeanDiffCL=lsmeandiffcl;
```

run;

If there are any missing data in the primary efficacy endpoint, the number of subjects, means, and standard errors by treatment group will be calculated from patients with observed data, while the LS means, difference in LS means and the corresponding CI will be calculated based on each particular missing data handling approach as described below.

A review of the residuals will be done to determine whether the normality assumption is met. If the normality assumption is not met, a rank ANCOVA model will be used to corroborate the result of the significance test. Details will be given below.

2.4.4.1.2 Missing data handling

Patients who permanently discontinue the study medication will be asked and encouraged to return to the clinic for all remaining study visits and the Study investigators should continue OCS dose

adjustment after treatment discontinuation, as guided by their medical judgment, including uptitration and down-titration in accordance with Table 2. The off-treatment OCS dose will be used in the primary analysis. During the study, only monotone missing pattern is expected. The number of patients with missing data will be summarized for each treatment group by reason of treatment discontinuation and the last time without missing data. The percent reduction for these patients will be summarized using descriptive statistics by treatment group and visit.

For statistical inference based on the main model, the following approaches will be used to handle the missing data:

Primary approach – pattern mixture model by multiple imputation

This approach will impute missing percent reduction of OCS dose at Visits 5 (Week 4), 7 (Week 8), 8 (Week 12), 9 (Week 16), 10 (Week 20) and 11 (Week 24), using multiple regression models. Imputation will be conducted sequentially by visit, since the imputation for each visit will incorporate information at prior visits. Specifically, the model for each visit will focus on the percent reduction of OCS dose at the visit as the response variable and include the following predictors: the covariates incorporated in the primary statistical model, including baseline eosinophil level subgroup, region (pooled countries), the treatment group, optimized OCS dose at baseline, and the percent reduction of OCS dose from baseline at all the prior visits. Of note, since per protocol a new dose, and therefore the corresponding percent reduction from baseline, if not missing should be one of three possible values corresponding to decreasing, maintaining, or increasing from the previous dose based on the titration Table 2, the imputed value for each missing percent reduction will be the one among the three possible values that is closest to the initially imputed predicted percent reduction from the imputation model. Forty imputations will be performed. For each imputation, the complete percent reduction of OCS dose at Week 24 will be analyzed using the main statistical model described above. LS means by the treatment groups and difference in the LS means will be obtained. Rubin's rule will be used to combine results from all the imputations into a single inference for each of the parameters. P-value and CI will be obtained for the treatment difference. The details of obtaining the observed OCS doses for each visit are described in the data handling convention section.

This approach will be implemented using procs MI and MIANALYZE with the following steps.

1. For the first visit among Visits 5, 7, 8, 9, 10 and 11 that has missing data on prescribed daily maintenance OCS dose, generate 40 imputed dataset, where the missing percent reduction of OCS dose at the visit is imputed from the model described above. Sample SAS code is provided below:

```
proc mi data=ocsdata nimpute=40 seed=&seed out=data_imp;
    class eosbgp2n cntygr1 trt01pn;
    var eosbgp2n cntygr1 trt01pn ocsb1 &ocspc_prior
    &ocspc_curr;
    monotone reg(&ocspc_curr);
run;
```

where $\&ocspc_curr$ is the percent reduction of OCS dose at the current visit/time, and $\&ocspc_prior$ includes the percent reduction of OCS at all the prior visits considered in the imputation. If the current visit is Visit 5 (Week 4), no prior percent reduction will be included. For each missing percent reduction data, the three possible values can be identified from titration Table 2 based on the dose at baseline and the dose immediately before the current visit. The imputed percent reduction will be the one closest to the predicted from the model. Of note dose increase beyond baseline level is possible and will follow the first row of the titration table. For each of the subsequent visits until Visit 11 (Week 24), similar imputation model will be built with the following sample SAS code:

```
proc mi data=data_imp nimpute=1 seed=&seed out=data_imp;
    by _imputation_;
    class eosbgp2n cntygr1 trt01pn;
    var eosbgp2n cntygr1 trt01pn ocsb1 &ocspc_prior
    &ocspc curr;
    monotone reg(&ocspc_curr);
run;
```

One seed will be used to generate random seeds for the MI at each visit.

2. Each of the 40 imputed datasets will be analyzed using the main statistical model. Sample code:

```
proc glm data= data_imp;
    by _imputation_;
    class eosbgp2n cntygr1 trt01pn;
    model ocspcw24 = ocsbl eosbgp2n cntygr1 trt01pn;
    lsmeans trt01pn / stderr;
    estimate 'Diff Dupilumab vs Placebo' trt01pn -1 1;
    ods output LSMeans=implsmeans Estimates=implsmeandiff;
run;
```

3. Applying Rubin's rule to combine analysis results (point estimates and variance) from 40 imputations using proc MIANALYZE for the LS means and difference in LS means between dupilumab and placebo. Sample code:

```
proc sort data=implsMeans; by trt01pn _imputation_;run;
proc mianalyze data= implsmeans;
    by trt01pn;
    modeleffects lsmean;
    stderr stderr;
    ods output ParameterEstimates=lsmeans;
run;
proc mianalyze data=implsmeandiff;
    modeleffects estimate;
    stderr stderr;
    ods output ParameterEstimates=lsmeandiff;
run;
```

Sensitivity analysis

Pattern mixture model by control-based multiple imputation

The same MI method as the primary approach will be used except that only data of patients in the control group will be used to fit the MI models and the treatment variable will not be incorporated as one of the covariates in the MI models. In Step 1 above, at each visit, missing data of patients in both dupilumab and control groups will be imputed using the models fitted with control patients. This approach assumes that at each visit the missing OCS percent reduction in both treatment groups has the same distribution as those observed in the control group conditional on the covariates in the MI models.

Worse of the last two observations carry forward

For the missing OCS dose at Week 24, the worse (higher) dose between the doses at the last two scheduled visits with available maintenance OCS doses during the treatment period will be used to impute the OCS dose at Week 24 to calculate the primary efficacy endpoint. If a patient drops out of study before Visit 5, the baseline dose (0% reduction) will be used. The main statistical model will be applied to the complete dataset after the imputation.

Tipping point analysis

Tipping point analysis will be conducted to evaluate the robustness of the primary analysis result. This will be conducted by sequentially increasing the imputed percent OCS reduction at Week 24 in the control group and decreasing the imputed values in the treatment group from the primary missing data handling approach. Specifically, for patients in the dupilumab group missing the endpoint, one sequentially subtracts 10% from each imputed value. For patients in the placebo group missing the endpoint, one sequentially adds 10% to each imputed value, until all the patients in all imputations reach their maximum possible percent reduction of OCS dose per protocol. The mean increase in the percent reduction of OCS dose from the original imputed values will be calculated to reflect the actual amount of shift in the placebo group, For each combination of increase in the placebo group and decrease in the dupilumab group, the new dataset will be analyzed and results will be combined using the same methods in Steps 2 and 3 of the primary missing data handling approach. The LS mean difference in percent reduction of OCS dose between the two treatment groups and the corresponding p-values will be reported.

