- *q* OCS titration during the OCS Optimization Phase can occur weekly following Visit 2 until the optimal OCS dose is determined and every 4 weeks during the OCS Reduction Phase but is not necessarily required to occur during a scheduled in-clinic visit.
- r At the EOT visit (Visit 11), the final OCS dose the patient is receiving needs to be documented; no adjustments to the OCS dose will be permitted (except for those patients who experience an asthma exacerbation).
- s Serum pregnancy test at Visit 1 and urine pregnancy tests at other visits. A negative result must be obtained at Visits 1 and 3 prior to randomization.
- t Hematology: hemoglobin, hematocrit, platelet count, total white blood cell count with 5-part differential count, and total red blood cell count. Serum chemistry: creatinine, blood urea nitrogen, glucose (only at Visits 3, 8, and 11), HbA1c, uric acid, total cholesterol, total protein, albumin, total bilirubin (reflex testing will be triggered by elevated bilirubin), alanine aminotransferase, aspartate aminotransferase, alkaline phosphatase, lactate dehydrogenase, electrolytes (sodium, potassium, chloride), bicarbonate, and creatine phosphokinase. Clinical laboratory testing at Visit 1 and Visit 10 (only for patients who planned roll over into a long-term study) includes hepatitis screen (HBsAg, HBsAb, IgM and IgG/total-HBcAb, and HCVAb), HIV screen (anti-HIV-1 and anti-HIV-2 antibodies), and ANA. Patients who are IgG/Total-HBc Ab positive and HBs Ag negative at Visit 1 must undergo HBV DNA testing prior to randomization to determine eligibility (only applicable for patients who plan to roll over into a long term study). Note: Anti-ds DNA antibody will be tested if ANA is positive (≥1:160 titer). At Visits 3 (randomization), 8, and 11, the blood sample should be taken with the patient in fasting state which means no intake of any food or drink except for water for at least 8 hours. If the visit can only be done at a different time of the day and the patient is not fasting, then he/she should be advised to eat a light meal and the site should document that serum chemistry was not obtained under fasting conditions.

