During this phase patients will remain on their optimized dose of OCS along with their baseline asthma medications.

OCS Reduction Phase (16 weeks)

The OCS dose should be down-titrated during this phase following a pre-determined schedule, provided in Table 2 that is based upon the optimized OCS dose identified during the OCS Optimization Period. Dose reductions may occur every 4 weeks which should allow the minimization of any carryover effects from the previous dose and reduce the risk for adrenal insufficiency. The last possible dose reduction can occur at Week 20. No down-titration beyond this time point is permitted.

Time course				ocs	dose (m	g/day)			
Optimized OCS dose	35	30	25	20	15	12.5	10	7.5	5
First dose reduction	25	20	15	10	10	10	5	5	2.5
+4 week	15	10	10	5	5	5	2.5	2.5	0
+4 week	10	5	5	2.5	2.5	2.5	0	0	
+4 week	5	2.5	2.5	0	0	0			
+4 week	2.5	0	0						

Table 2 - Oral corticosteroid titration schedule during the Oral Corticosteroid Reduction phase

OCS=oral corticosteroid

The reduction in OCS dose should occur per the schedule unless the patient meets defined criteria indicating that it is not acceptable for the patient to reduce the dose. A clinical assessment should be completed prior to each dose reduction. Primary reasons for not following the scheduled dose reduction include:

- Mean morning PEF <70% of baseline stability limit
- Forced expiratory volume in 1 second (FEV1) 20% reduction from baseline stability limit
- Rescue medication (metered dose inhaler) use requiring 4 or more puffs/day above the mean baseline value for any 2 consecutive days in the prior week, or 12 puffs or more on any 1 day in the prior week

- Change in ACQ-5 score \geq +0.5 from the prior month OCS dose assessment
- Clinically significant asthma exacerbation
- Clinically significant event, based on investigator judgment that requires treatment by OCS dose adjustment

The Investigator should decide, depending on the reason for not reducing the OCS dose per schedule, whether to maintain or increase his/her current OCS dose by 1 step.

Maintenance Phase (4 weeks)

Patients will be maintained for the last 4 weeks of the Randomized Treatment period on the same OCS dose established at Week 20. However, when any of the above criteria for not reducing OCS dose is met, the Investigator should decide whether to maintain or increase the current OCS dose accordingly.

Oral Corticosteroid Dose after an Asthma Exacerbation

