For the OCS dose used for efficacy assessment, the baseline dose and the final dose at Week 24/Visit 11 are recorded in the corresponding CRF pages. OCS doses at Visits 5, 7, 8, 9, and 10 during the treatment period will be obtained from the prescribed dose recorded in ediary based on the date of OCS adjustments recorded in the 'Oral Corticosteroid Dose Adjustment - Treatment Phase' eCRF pages associated with each visit. If it is recorded that there was no dose adjustment for a visit, the dose of the previous visit will be considered maintained for the current visit and thus carried forward. For patients permanently discontinue treatment before Week 24/Visit 11, any dose adjustment recorded at the Early Treatment Discontinuation visit will be assigned to the regular visit after the last on treatment visit. In case there were more than one adjustments associated with one visit, the last dose will be used for the visit.

For the other efficacy assessments, the reference date for the derivation of relative days of events or findings will be the randomization day. If a patient receives IMP prior to the randomization by

Statistical Analysis Plan SAR231893-EFC13691 - dupilumab 18-May-2017 Version number: 1

mistake, the reference date of efficacy assessment will be the date of the first IMP administration for that patient. Table 9 assigns all scheduled measurements of efficacy endpoints for visits to the appropriate visit window. The ACQ-5 questionnaires planned for the weeks between visits will not be assigned to the visits. In the event of multiple measurements of the same test in the same window, the one closest to the targeted visit date will be used for the by-visit summary. If they are at the same distance to the target day, the latest one will be used.

Time windows for						
Visit	Target Day	Spirometry, ACQ-5, ACQ-7	Post-bronchodilator FEV ₁ , AQLQ(S), EQ-5D-5L, HADS, SNOT-22	Airway hyperresponsiveness (selected study sites within Canada)		
Visit 3 (Week 0)	1	-14-1 ⁻	1-	1-		
Visit 4 (Week 2)	15	1+-21				
Visit 5 (Week 4)	29	22-35				
Visit 6 (Week 6)	43	36-49				
Visit 7 (Week 8)	57	50-70				
Visit 8 (Week 12)	85	71-98	1+-126			
Visit 9 (Week 16)	113	99-126				
Visit 10 (Week 20)	141	127-154				
Visit 11 (Week 24)	169	155-182	127-210	1+		
Visit 12 (Week 28)	197	183-210				
Visit 13 (Week 32)	225	211-238				
Visit 14 (Week 36)	253	>238	>210			

Table 9 – Time window for efficacy variables

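### The primary imputation permits a dose decrease from Week 20 to Week 24 that SAP 1.4 and the protocol exclude

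*SAP*

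**What the plan says.** SAP 2.4.4.1.2 (primary missing-data approach) imputes the percent OCS reduction visit by visit at Visits 5, 7, 8, 9, 10 and 11 (Weeks 4, 8, 12, 16, 20 and 24). A regression draw is replaced by the nearest of a short list of candidates: "one of three possible values corresponding to decreasing, maintaining, or increasing from the previous dose based on the titration Table 2". Step 1 says that "the three possible values can be identified from titration Table 2", from the baseline dose and the preceding dose. It then carries the method on: "For each of the subsequent visits until Visit 11 (Week 24), similar imputation model will be built". No exception is made for Visit 11.

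SAP 1.4 says of the reduction phase: "The last possible dose reduction can occur at Week 20. No down-titration beyond this time point is permitted". For the maintenance phase, Weeks 20 to 24, it says that when an interruption criterion is met "the Investigator should decide whether to maintain or increase the current OCS dose accordingly". The protocol summary and protocol sections 8.2.2.2 and 10.1.2.3 also place the last reduction at Week 20. Footnote r of the protocol flow chart allows no adjustment at Visit 11 except after an exacerbation.

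**The concern.** The SAP justifies its candidate list by what the protocol allows. At Visit 11, the visit that defines the primary endpoint, one of the three candidates is not allowed. A programmer who follows the text will generate a step the trial excludes. One who notices the conflict must improvise inside a prespecified confirmatory analysis.

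The reach is wide. The same imputed datasets, or the same method, serve the control-based imputation, the tipping-point starting values, the rank ANCOVA, the on-treatment analysis, the subgroup analyses, the absolute reduction and every OCS responder endpoint. The primary endpoint and all four ranked secondary endpoints are therefore touched.

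**Working it through.** **Plan's own figures.** With n = 90 per arm, difference 27, SD 50 and two-sided α = 0.05 (SAP 1.3): 27 / (50 × √(2/90)) = 27 / 7.454 = 3.622, and Φ(3.622 − 1.960) = 95.2% (95.0% by noncentral t), against 94% stated. For 33% v 54%, power is 81.6% against 81% stated. Both are close. The point does not depend on them; they only give the scale.

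**Is the Week 24 decrease merely the Week 20 step counted late?** No. SAP 2.5.4 says: "OCS doses at Visits 5, 7, 8, 9, and 10 during the treatment period will be obtained from the prescribed dose recorded in ediary". It uses the adjustment recorded for each visit, so the Visit 10 dose already contains any Week 20 change. The protocol gives five chances to reduce (Weeks 4, 8, 12, 16, 20); the imputation gives six.

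**Does a sixth chance create new final values?** Table 2 has 5, 5, 5, 4, 4, 4, 3, 3 and 2 steps for baseline doses 35, 30, 25, 20, 15, 12.5, 10, 7.5 and 5 mg, 35 in total. Five reductions reach the bottom of every column: 2.5 mg (92.9% reduction) from 35 mg, and 0 mg (100%) from every other dose. A sixth adds no new final value.

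**Does it change what a given patient can reach?** Yes. Counting every dose state possible at the last observed visit:

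| Last observed | Possible states | States where the rule reaches a lower Week 24 dose than permitted |
|---|---|---|
| Week 4 | 18 | 3 |
| Week 8 | 27 | 9 |
| Week 12 | 35 | 17 |
| Week 16 | 41 | 26 |
| Week 20 | 44 | 35 (the other 9 are at the floor) |

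**Effect on responder status.** Of the 35 one-step decreases (7.1 to 50 points, median 25), 9 cross the 50% line, 9 cross below 5 mg/day and 8 reach 0 mg. Two cross both of the first two lines, so 9 + 9 + 8 − 2 = 24 change at least one outcome. For example, a patient on 10 mg at baseline and still on 10 mg at Week 20, imputed to 5 mg at Week 24, becomes a 50% responder.

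**How often would it happen?** If a decrease is worth D points, the predicted change is m and the residual SD is s, the draw snaps down with probability 1 − Φ((D/2 − m)/s). For D = 25 and s = 10 this is 1 − Φ(1.25) = 10.6% at m = 0, and 1 − Φ(1.75) = 4.0% at m = −5. It is zero for patients at the floor.

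The sequential imputation was simulated with and without the Visit 11 decrease, using an assumed dose mix, assumed titration rates and dropout of 2-15% per arm, 10 imputations and 150 trials per setting. The settings below had arm-mean differences of about 34-36 points and SD 51-52:

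| Assumed dropout, placebo / dupilumab | Week 24 residual SD | Imputed Week 24 values that are decreases | Mean shift in treatment difference | Largest shift in one trial |
|---|---|---|---|---|
| 5% / 10% | 8.7 | 4.7% | +0.06 | 0.35 |
| 10% / 5% | 8.7 | 4.0% | −0.02 | 0.27 |
| 2% / 15% | 8.7 | 4.7% | +0.13 | 0.42 |
| 10% / 10% | 13.0 | 6.8% | +0.02 | 0.50 |
| 5% / 15% | 13.0 | 7.6% | +0.21 | 0.93 |

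The 50% responder difference moved by at most about 0.1 percentage point. Two further simulations under other assumptions gave 3-7% (dropout 5-25%) and 1.5-6.5% (dropout 10%) of imputed Week 24 values, with a shift in the treatment difference below 0.1 point.

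**Arm level.** At 10% dropout the mean reduction among imputed patients rose by 0.6-1.7 points and their 0 mg rate by 0.8-1.7 points. Over all patients that is 0.10 × (0.6 to 1.7) = 0.06-0.17 point and 0.10 × (0.8 to 1.7) = 0.08-0.17 point. A crude ceiling for one arm is 15% missing × 25% snapped down × 50 points = 1.9 points.

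**Against the planned effect.** Moving the difference by 0.2 point changes the 95.2% power to 94.9% (26.8) or 95.4% (27.2).

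**The case against.** **The final values are reachable.** A reader might infer that the imputation creates reductions no patient in the trial could have. The enumeration rules that out: each imputed reduction is one that another patient with the same baseline dose could reach by Week 20. Only the step, given the patient's own history, is excluded.

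**It does not favour dupilumab.** Each excluded step improves that patient's imputed outcome, so a reader might infer a bias toward active treatment. The snapping rule is the same in both arms. In simulation the shift was near zero with equal dropout, and with unequal dropout its sign followed the arm that lost more patients. The documents say nothing about which arm that would be.

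**Titration continues off treatment.** SAP 1.4 and protocol 10.3.4 let investigators keep adjusting OCS after IMP is stopped. But they refer to Table 2, and protocol 11.4.2.1 ties this to section 8.2.2.2, which contains the Week 20 limit. Neither gives leave to reduce later.

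**The model already learns the ban, and removing the decrease may not help.** The Week 24 regression is fitted to patients who could not reduce, so decreases come only from residual noise, and removing one side truncates that noise. This has some force. In simulation against known complete data, with dropout spread over all visits, the mean reduction among dropouts was 54.5 under the SAP rule, 53.4 without the decrease and 54.3 in truth in one setting; in another it was 53.3, 51.7 and 53.7. Both rules under-imputed 0 mg, and removing the decrease lowered it by a further 0.2-1.8 points, while the 50% responder rate came closer to the truth by 0.2-1.4 points. The advantage for the mean arises because errors at earlier visits happen to offset the Week 24 error. With only Week 24 missing, removing the decrease brought the mean and the 50% responder rate closer to the truth, with mixed results for below 5 mg and 0 mg. An accidental offset is not a reason to keep an excluded value.

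**Other analyses protect the result.** The worse-of-last-two and dropouts-as-non-responders analyses do not use the rule, and the tipping-point analysis moves imputed values in 10-point steps. This supports the view that the impact is low, but it leaves the primary specification uncorrected.

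**Conclusion.** The contradiction is in the text and needs no simulation: SAP 2.4.4.1.2 offers a Visit 11 decrease as allowed by the protocol, and no passage allows one. The label is wrong as written, low numerical impact.

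The sizes rest on assumed dropout, dose mix and titration rates, because the documents give none. Within those ranges, roughly 2-8% of imputed Week 24 values are affected. The treatment difference moves by about 0.2 point or less on average (at most 0.93 in one simulated trial), against a planned 27. The rises in the 0 mg rate and in mean reduction quoted for imputed patients apply to those patients only; they are not shifts in the trial result, where at 10% dropout arm means move by about 0.1 point.

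The documents also differ on whether a dose may rise after Week 20: some passages let the investigator increase it in the maintenance phase, while protocol 8.2.2.2 also says there are no further adjustments. Those passages need reconciling with each other. The point here does not depend on the answer, since none of them permits a decrease.

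**What to change.** In SAP 2.4.4.1.2, reconcile the imputation candidates with SAP 1.4 by adding a sentence that a decrease from the Visit 10 dose is excluded from the candidate values at Visit 11. State that this applies to the primary, control-based and on-treatment imputations. Analyses that reuse those datasets then inherit it.

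The cost is one sentence and one condition in the program. No new data are needed, and the estimand, the ANCOVA model, the number of imputations and the testing order stay as they are.

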1 OVERVIEW AND INVESTIGATIONAL PLAN

1.1 STUDY DESIGN AND RANDOMIZATION

This is a multinational, multicenter, randomized, double-blind, placebo-controlled study assessing the effect (efficacy and safety) of dupilumab administered subcutaneously (SC) for a maximum of 24 weeks in patients with severe steroid-dependent asthma.

The clinical trial will be divided into the following periods:

- Screening and oral corticosteroids (OCS) Optimization period (from 3 to up to 8 weeks [up to 10 weeks for patients experiencing an asthma exacerbation that requires a change in OCS dose to allow for 2 weeks of stabilization prior to randomization]): to determine a patient's eligibility status and to ensure that patients enter the treatment period on the lowest dose of OCS that will manage their symptoms
- Treatment period (24 weeks): includes a 4-week induction phase, a 16-week OCS reduction phase, and a 4-week maintenance phase
- Post-treatment/Follow up period (12 weeks): to monitor a patient's status after completing/withdrawing from study drug treatment for patients not participating in the long-term extension study.

Patients who meet the entry criteria will be randomized via Interactive Response Technology (IRT) in a 1:1 ratio to receive a 600 mg loading dose followed by 300 mg once every 2 weeks (q2w) of dupilumab or matching placebo, respectively. Randomization will be stratified by optimized OCS dose at Week 0 ($\leq 10 \text{ mg/day}$, >10 mg/day) and country.

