1.3 DETERMINATION OF SAMPLE SIZE

The sample size estimation is based on the comparison between dupilumab doses versus placebo with regard to the primary endpoint, percentage reduction of OCS dose at Week 24 compared with the baseline dose, and a key secondary endpoint, proportion of patients achieving a reduction of 50% or greater in their OCS dose compared with baseline at Week 24, while maintaining asthma control. For the primary endpoint, assuming a common standard deviation of 50%, with 90 randomized patients per group, the study will have 94% power to detect a treatment difference of 27% (1) at the 2-tailed significance level of α =0.05. For the key secondary endpoint, with the same sample size of 90 randomized patients per group, the study will have 81% power to detect a difference, at the 2-tailed significance level of α =0.05, in the proportion of patients achieving reduction of 50% or greater in their OCS dose, assuming that the proportions are 33% in the placebo group, compared to 54% in the dupilumab group (2).

Calculations were made using nQuery Advisor 7.0.

Recruitment of patients whose eosinophil level is below 150 cells/ μ L will stop when approximately 46 (25% of the total sample size) of such patients are randomized. Recruitment will continue with patients whose eosinophil (EOS) level is greater than or equal to 150 cells/ μ L until reaching the total sample size of 180. In addition, the number of patients receiving 5 mg OCS at Visit 3 will be limited to approximately 54 patients (approximately 30% of the study population).

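### If Week 24 doses are missing, the pooled primary analysis ignores the ANCOVA's finite degrees of freedom, so its confidence interval is slightly too narrow

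*SAP*

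**What the plan says.** SAP 2.4.4.1.1 defines the primary analysis as an ANCOVA of percentage reduction in OCS dose at Week 24, in which the "treatment difference will be tested at the 2-sided significance level of α =0.05".

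If Week 24 data are missing, SAP 2.4.4.1.2 imputes them sequentially by visit: "Forty imputations will be performed". Each completed dataset is analysed by PROC GLM with "model ocspcw24 = ocsbl eosbgp2n cntygr1 trt01pn". Step 3 then applies Rubin's rule to "combine analysis results (point estimates and variance) from 40 imputations using proc MIANALYZE for the LS means and difference in LS means".

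Two sample calls are given for step 3. The one for the treatment difference begins "proc mianalyze data=implsmeandiff"; the other pools the LS means by treatment group. Each contains only the effect, standard-error and output statements, plus a BY statement in the LS-means call. Neither has EDF=. The text names no complete-data degrees of freedom and no small-sample adjustment, and SAP 2.5.7 (statistical technical issues) lists nothing.

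**The concern.** Without EDF=, PROC MIANALYZE uses Rubin's large-sample degrees of freedom, which depend only on the number of imputations and the share of information that is missing. With 40 imputations and little missing information the result runs into the thousands. An analysis with missing data would then claim more degrees of freedom than the same ANCOVA on a complete dataset, and would use a near-normal critical value.

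The direction is fixed: omitting the option always gives the smaller critical value, hence a narrower interval and a smaller p-value. This affects the primary 5% test.

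It also leaves the plan uneven. The worse-of-last-two-observations sensitivity analysis fits the same model to a single dataset and so uses the residual degrees of freedom. For the other continuous endpoints, which have no multiplicity control, SAP 2.4.4.4.3 specifies a Kenward-Roger adjustment.

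**Working it through.** **Inputs from the documents**
- Two-sided alpha 0.05 (SAP 2.4.4.1.1); m = 40 imputations (SAP 2.4.4.1.2).
- Sample size (SAP 1.3): "assuming a common standard deviation of 50%, with 90 randomized patients per group". Allocation is 1:1 (SAP 1.1).
- Model parameters: intercept 1, baseline dose 1, eosinophil group 1, region 2 (three regions, SAP 2.5.6), treatment 1. Total 6.

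**Assumed.** The fraction of missing information λ is not in the documents. I use 1% to 20% as the working range and show 50% as an extreme.

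**The plan's own figure.** SAP 1.3 says "the study will have 94% power to detect a treatment difference of 27" percentage points. The standard error is 50 × √(2/90) = 7.45 points. Power is 95.2% by the normal formula and 95.0% by noncentral t with 178 df, within about a point of the stated 94%.

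**Complete-data degrees of freedom.** 180 − 6 = 174, with 97.5% t quantile 1.9737 against the normal 1.9600.

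**Default pooled df (Rubin).** (m − 1)/λ². At λ = 5%: 39/0.0025 = 15,600. This exceeds 174 whenever λ < √(39/174) = 0.473.

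**Adjusted df (Barnard-Rubin, as EDF=174 would give).** 1/(1/df_Rubin + 1/df_obs), with df_obs = (175/177) × 174 × (1 − λ). At λ = 5%: df_obs = 163.4, and 1/(1/15,600 + 1/163.4) = 161.7.

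| λ (assumed) | Default df | Adjusted df | Default critical value | Adjusted critical value | Ratio of widths, adjusted/default | Tail area of default cut-off under adjusted t |
|---|---|---|---|---|---|---|
| 1% | 390,000 | 170 | 1.9600 | 1.9740 | 1.0072 | 0.0516 |
| 5% | 15,600 | 162 | 1.9601 | 1.9747 | 1.0075 | 0.0517 |
| 10% | 3,900 | 149 | 1.9606 | 1.9760 | 1.0079 | 0.0518 |
| 20% | 975 | 121 | 1.9624 | 1.9798 | 1.0089 | 0.0520 |
| 50% | 156 | 55 | 1.9753 | 2.0037 | 1.0144 | 0.0532 |

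**On the outcome scale.** At the design standard error the 95% half-width is 7.45 × 1.9600 = 14.61 points with the normal quantile and 7.45 × 1.9737 = 14.71 with t on 174 df, a difference of 0.1 point. At λ = 5% and the design effect, power is 94.1% by default and 93.9% with the adjustment. Default p-values of 0.05, 0.04 and 0.01 become 0.0517, 0.0416 and 0.0109.

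**Null simulation.** 8,000 runs, normal data, N = 180, m = 40, values missing at random in both arms, and an earlier visit correlated 0.8 with the outcome. Rejection rates, default against adjusted:
- 5% of outcomes missing (median λ 1.9%): 5.06% and 4.94%.
- 15% missing (median λ 6.2%): 4.89% and 4.80%.

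The Monte Carlo standard error is √(0.05 × 0.95/8,000) = 0.24 percentage points.

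**The case against.** The strongest reply is that the code does what the text says. Rubin's original rule uses the large-sample degrees of freedom, the Barnard-Rubin form is a later refinement, and the code is headed as a sample, so the final program may differ. Part of this stands: code and text do not contradict each other. But the sample code is the only implementation specified, and nothing in the SAP overrides the default. That default is a property of the software and is not written in the documents.

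A reader might infer that the true type I error is 5.2%. The documents do not support that. The 5.2% is the tail area of the default cut-off under one approximate t reference. In the simulation no default rate is distinguishable from 5%, and at 15% missing it falls below 5%, although the simulation is too coarse to exclude a shift this small. The real outcome is also discrete, imputed values are moved to one of three permitted doses, and the SAP itself allows for non-normal residuals. An exact error rate cannot be claimed.

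A reader might also infer that the primary interval is affected whatever happens. It is not. With complete Week 24 data, PROC GLM uses its residual degrees of freedom. The plan also limits missingness by encouraging patients who stop study drug to attend all remaining visits and by using their off-treatment dose.

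Finally, the effect does not matter to the design. The design effect gives a statistic of 27/7.45 = 3.6, far from the cut-off. That stands, and it is why this is a minor point.

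**Conclusion.** The point holds, as a small one. If Week 24 doses are missing and the step 3 code is run as written, the pooled degrees of freedom exceed what the ANCOVA can supply for any missing information below about 47%. Over an assumed 1% to 20%, the 95% interval is about 0.7% to 0.9% too narrow. The primary conclusion could change only if the default p-value lay between about 0.048 and 0.050. The error bars are wrong as written, though slightly, and severity is at the nice-to-have level. The figures assume 180 analysed patients, the six-parameter model and the stated range of missing information.

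**What to change.** Add EDF= to both PROC MIANALYZE calls in SAP 2.4.4.1.2, step 3, set to the actual error degrees of freedom of the fitted ANCOVA. That is 174 only if exactly 180 patients are analysed. The protocol summary says approximately 180, so the value should be read from the model and not hard-coded. Add a sentence to the text naming the small-sample adjustment.

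Carry the change to the other analyses that pool ANCOVA results in the same way:
- control-based imputation and tipping point (2.4.4.1.2); the tipping-point analysis reports p-values over a grid of shifts, some of which may fall near 0.05;
- on-treatment (2.4.4.1.3);
- subgroup models (2.4.4.1.4), each with its own error degrees of freedom;
- absolute reduction (2.4.4.2.2).

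The pooled logistic analyses do not need it. The cost is one option per call and a line of text. Fixing it before unblinding also removes a later choice of degrees of freedom.
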